## SYNOPSIS

Title of Study	Randomized Trial Comparing A Dual Action Pneumatic Compression System against Multi-Layer Bandaging Systems: A non-inferiority study
Protocol Date	27 September 2016
Protocol Version	V 2.0
Name of Sponsor	Tactile Medical™
Investigational Product	ACTitouch Adaptive Compression System
Primary Endpoint	Percentage of ulcer area reduction at 16 weeks, comparable
Secondary Endpoint	HRQOL; outpatient cost per subject
Objectives: Demonstrate the following when comparing ACTitouch Adaptive Compression to multi-layer bandaging: 
 
• Comparable rate of healing
 
• Greater improvement in QOL
 
• Lower overall cost of care; lower resource utilization (in clinic time; clinic charges; patient treatment burden)
 
	
METHODOLOGY	
Study Design	Open label, non-inferiority, two arm, prospective, stratified, multi-center, randomized controlled trial (RCT)
Treatments	Daily ACTitouch usage; at least 12 hours sustained mode; two hours of Intermittent Pneumatic Compression (IPC) mode Multi-Layer Bandage (MLB): 24 hours except during clinic visits
Treatment Duration	Run-in – 2 Weeks Study treatment duration – 16 Weeks Follow Up – 3 months (Subjects in the ACTitouch arm who heal during the treatment period.)
SUBJECT POPULATION	
Number Planned	204 randomized subjects; 102 in each study arm
Major Inclusion/ Exclusion Criteria	Inclusion: 
 
• Subject must be <math>\geq 18</math> years of age or legal age at the time of enrollment.
 
• Chronic venous insufficiency confirmed by ultrasound within previous 12 months or prior to randomization.
 
• Must have at least one of the following within the past 6 months: 
 
○ Dorsalis Pedis (DP) systolic pressure <math>\geq 80</math>mmHg for diabetic patients or <math>\geq 60</math>mmHg for non-diabetic patients on study limb
 
○ Posterior Tibial (PT) systolic pressure <math>\geq 80</math>mmHg for diabetic patients or <math>\geq 60</math>mmHg for non-diabetic patients on study limb
 
○ Transcutaneous partial pressure oxygen (TcP02) <math>> 30</math>mmHg
 
○ Great toe systolic pressure <math>> 40</math>mmHg
 
 
 
• Active ulceration (CEAP classification of C6).
 
• Ulcer duration: Non healing VLU <math>\geq 1</math> month but not greater than 24 months.
 
• Ulcer size <math>\geq 2\text{cm}^2 \leq 50\text{cm}^2</math>.
 
• Three or fewer separate full thickness ulcers on the study limb. 
 
○ Sum of the ulcer areas on the study limb must be <math>\leq 50\text{cm}^2</math> to participate in the study.
 
 
 
• Must be able and willing to provide informed consent prior to study
 

	
participation.
 
Exclusion:
 
 
• Target ulcer or any other ulcer on the study limb involves exposure of tendon, muscle, or bone.
 
• Treatment of the target ulcer with living cellular therapy within 30 days of the time of projected randomization.
 
• Endovenous ablation or other venous surgery within two weeks of enrollment. 
 
○ Venous ultrasound must be completed after procedure to determine whether there is still venous insufficiency at the time of enrollment.
 
 
 
• Acute deep vein thrombosis (DVT) or pulmonary embolism (PE) within the last 3 months.
 
• Acute thrombophlebitis within the last 6 weeks.
 
• History of pulmonary edema or decompensated congestive heart failure within 6 weeks of screening.
 
• Currently has an active infection of the skin on target limb such as cellulitis requiring antibiotics.
 
• History of target limb cancer within the last 2 years with the exception of treated non-melanoma skin cancer unless ulcer biopsy performed at screening is negative for neoplasia.
 
• Active cancer receiving chemotherapy and/or radiation therapy.
 
• Poorly controlled diabetes with an HbA1c value of > 12% within the past 3 months.
 
• Changes to medications that affect edema within the last 30 days.
 
• Use of systemic corticosteroids requiring daily administration at doses greater than 5 mg of Prednisone per day or equivalent for greater than 2 weeks.
 
• Currently pregnant or trying to become pregnant.
 
• Inability or unwillingness to participate in all aspects of study protocol.
 
 
Exclusions after a 2 week run-in:
 
 
• If ulcer area has decreased by greater than 30% compared to baseline area, the subject will be removed from the study.
 
• Ulcers measuring less than 1.5cm^2 after the run in.
 
• Ulcers increasing in size greater than 50% after run.
 
• Any ulcer appearing to have evidence of infection.
 
• If the sum of the ulcer areas on the study limb is > 50cm^2 the subject is not eligible to participate in the study.
 

ASSESSMENTS	


Efficacy [If applicable]
	
Group 1: Multi-Layer Bandage
 
 
• Will be seen in clinic once per week for: 
 
○ Wound assessment
 
○ wound dressing changes, debridement, if necessary, as determined by the treating study investigator
 
○ wound tracing; photo
 
○ limb volume measurements
 
 
 
• Subjects will be instructed to wear the MLB 24 hours daily, except upon removal and re-application during weekly clinic visits with debridement as determined necessary by PI
 
 
Group 2: ACTitouch Adaptive Compression System
 
 
• Will be seen in the clinic at weeks 1, 2, 4, 6, 9, 12, 16 during the treatment period. Subjects who experience complete healing of the study VLU will return to the investigational site 1, 2 and 3 months post heal. 
 
○ wound assessment, as applicable
 
○ wound dressing changes, debridement, if necessary, as determined by the treating study investigator
 
○ wound tracing; photo, as applicable
 
○ limb volume measurements
 
 
 
• Subject will be instructed to wear the AT in sustained mode for a minimum of 12 hours per day plus 2 hours IPC mode.
 

Safety
	
Adverse event monitoring  Subject interview  Physical examination

## 1.0 Contact Information:

### 1.1 Sponsor Contact Information Tactile Medical™

### 1.2 Study Principal Investigator Information

## 2.0 Abbreviations:

ABI	Ankle Brachial Index
AE	Adverse Event
CEAP	Clinical-Etiology-Anatomy-Pathophysiology
CFR	Code of Federal Regulations
CRFs	Case Report Forms
CVD	Chronic Vascular Disease
CVI	Chronic Venous Insufficiency
DSMB	Data Safety Monitoring Board
DVT	Deep Vein Thrombosis
FDA	Food and Drug Administration
GCP	Good Clinical Practices
HRQOL	Health-Related Quality of Life
ICH	International Conference on Harmonization
IPC	Intermittent Pneumatic Compression
IRB	Institutional Review Board
ITT	Intent-to-Treat
MLB	Multi-Layer Bandaging
MITT	Modified Intent-to-Treat
QOL	Quality of Life
RCT	Randomized Controlled Trial
SAE	Serious Adverse Event
SD	Standard Deviation
U/S	Ultrasound
VLU	Venous Leg Ulcer
VSU	Venous Stasis Ulcer
IWRS	Web-Based Randomization Process

\*The term ulcer and wound are used interchangeably throughout this document.

### **3.0 Introduction:**

#### **3.1 1 Background and Rationale:**

Up to 1% of the adult population in developed countries will suffer from leg ulceration during their lifetime. The most severe form of CVI is when limb ulceration occurs due to chronic venous hypertension. It is estimated that the prevalence of venous leg ulceration (VLU) is between 1 and 1.5 million patients in the United States.

It is important to address the underlying hemodynamic problem associated with chronic venous insufficiency rather than focusing solely on wound healing. Treatment for chronic venous disease relies on provision of adequate external compression therapy to diminish venous hypertension, as these therapies diminish progressive dilation of incompetent veins, may help close the damaged valves, and diminish the accumulation of extravascular fluid. Compression is a key component of treatment guidelines for the management of VLU.

The current standard of care in the treatment of VLUs is wound management in conjunction with compression therapy to promote venous return and reduction in edema. Options for limb compression treatment include compressive garments, use of multi-layer bandage systems, and paste bandage systems. Despite the inclusion of high strength compression in numerous VLU treatment guidelines, it is estimated that as many as 50% of VLUs never receive this type of therapy. In part, the reason for poor utilization of compression therapy is that most patients find the therapy difficult to use, due to difficulties in applying compression garments and/or pain or discomfort associated with use of the garment itself. To date, compression bandaging remains the most commonly used therapy in the treatment of VLUs.

Therefore, effective compression treatment must be easy to use (don and doff) and must be comfortable as key factors likely to increase patient compliance. Intermittent pneumatic compression (IPC) treatment is one alternative. IPC was introduced as an adjunct treatment for VLU in 1981 which led to growing support for IPC as a treatment modality for patients with VLUs. IPC is a mechanical method of delivering compression that uses an air pump to periodically inflate/deflate bladders incorporated into sleeves which envelop the limb.

[figure not shown]
Published studies have demonstrated significant hemodynamic and hematologic improvement with IPC, as well as increases in ulcer healing rates when IPCs are used with standard compression therapy.

Harding et al. compared the efficacy and tolerability of the ACTitouch device to that of a conventional multi-layer bandaging system when treating VLUs. In this trial, the ulcer healing rate between the ACTitouch group and the conventional four-layer system group was similar. However, the ACTitouch performed significantly better in several key areas related to patient quality of life including, exudate management, skin protection, removal ease, bathing, and sleep comfort.

This study provides evidence to suggest that the ACTitouch system is as effective as four layer bandaging systems in healing venous leg ulcers, but is better accepted and achieves higher patient-reported quality-of-life scores in these challenging patients.

### 3.2.2 Device Descriptions:

**ACTitouch** – ACT - A d a p t i v e C o m p r e s s i o n T h e r a p y D e l i v e r y S y s t e m (Tactile

**PROFORE** (Smith & Nephew, Hull, United Kingdom) is a multi-layer compression bandaging system developed to apply sustained graduated compression for the management of venous leg ulcers and associated conditions. Four-layer compression bandaging is often the first choice in treatment for venous leg ulcers.

The four-layer system consists of a single layer of orthopedic wool applied in a spiral from toe to knee, followed by a crepe bandage applied in a spiral, an elastic long stretch bandage applied by the figure of eight method and finally a cohesive bandage applied in a spiral (Appendix B). PROFORE provides approximately 40mmHg pressure at the ankle decreasing to 17mmHg at the knee.

**Coban™ 2 Compression System** (3M Health Care, St. Paul, MN, USA) is composed of two latex free layers that combine to create an inelastic sleeve conforming to the limb contour to provide a consistent proper pressure profile to

reduce edema. The Coban 2 compression system is indicated for patients with venous leg ulcers, lymphedema, and other conditions where compression therapy is appropriate.

The two-layer system consists of an inner “comfort” layer made of a polyurethane foam and cohesive bandage. The outer layer is a cohesive bandage, designed to provide graduated compression. Inner and outer layer cohere to each other to reduce slippage. Application of the compression system should be done according to the manufactures instructions as outlined in the Instructions for Use (Appendix C).

#### **4.0 Study Objectives:**

The primary study objectives:

Test non-inferiority of chronic VLU area reduction at 16 weeks with ACTitouch therapy compared to a standard regimen of multi-layer bandaging.

[figure not shown]
The secondary study objectives:

Assessment of the effect of the ACTitouch compared to a standard regimen of multi-layer bandaging at 16 weeks on health related quality of life (HRQOL) and outpatient costs.

[figure not shown]
#### **5.0 Study Design:**

The study is a two arm, open label, non-inferiority, prospective, stratified, multi-center, RCT. As part of screening there will be a two week run in period measuring the VLU initial treatment response. The study is designed to evaluate percentage of ulcer area reduction in venous leg ulcer patients comparing ACTitouch to multi-layer bandaging during the 16 week treatment phase.

[figure not shown]
## Run In Period – Two Week Treatment Response

Treatment Period (16 weeks)

Follow Up Period:

#### 5.1.1 Study Endpoints:

##### 5.1.1.1 Primary Endpoints:

The primary clinical endpoint:

- Percentage of ulcer area reduction at 16 weeks

##### 5.1.1.2 Secondary Endpoints:

The secondary clinical endpoints will include the following:

- Improvement in HRQOL
- Outpatient costs per subject
- Complications

#### 5.2.2 Subject Selection:

This is a community based trial. The study population will be drawn from patients who have chronic non-healed VLU's of at least one (1) month prior to the start of the study. Only patients who meet the criteria listed below will be considered for participation. A minimum of 204 subjects will be enrolled at approximately 30 centers in the United States.

##### 5.2.1 Inclusion Criteria:

- Subject must be  $\geq 18$  years of age or legal age at the time of enrollment.

- Chronic venous insufficiency confirmed by ultrasound within previous 12 months or prior to randomization.
  - If a study subject has bilateral CVI, the limb that possess the largest ulcer meeting study criteria will be used as the study treatment limb for evaluation and documentation throughout the study. Non-study limbs will receive standard of care treatment as determined by the treating clinician.
- Must have at least one of the following within the past six months:
  - Dorsalis Pedis (DP) systolic pressure  $\geq 80\text{mmHg}$  for diabetic patients or  $\geq 60\text{mmHg}$  for non-diabetic patients on study limb
  - Posterior Tibial (PT) systolic pressure  $\geq 80\text{mmHg}$  for diabetic patients or  $\geq 60\text{mmHg}$  for non-diabetic patients on study limb
  - Transcutaneous partial pressure oxygen (TcPO2)  $> 30\text{mmHg}$
  - Great toe systolic pressure  $> 40\text{mmHg}$
- Active ulceration (CEAP classification of C6)
  - VLU is defined by open skin lesion of the leg or foot that occurs in an area affected by venous hypertension.
- Ulcer duration: Non healing VLU  $\geq 1$  month but not greater than 24 months.
- Ulcer size  $\geq 2\text{cm}^2 \leq 50\text{cm}^2$ 
  - If there are multiple ulcers on the study limb, the largest ulcer will be used as the study treatment ulcer for evaluation and documentation throughout the study. If two ulcers are separated by no more than one centimeter of normal skin, their areas will be added together for study purposes.
- Three or fewer separate full thickness ulcers on the study limb.
  - Sum of the ulcer areas on the study limb must be  $\leq 50\text{cm}^2$  to participate in the study.
- Leg circumferences within the following range:
  - Ankle – 12 to 44cm
  - Calf – 22 to 60cm
  - Below knee – 22 to 68cm
- Must be able and willing to provide informed consent prior to study participation.

5.2.2 Exclusion Criteria: Subjects will be ineligible for this study if they meet any of the criteria described below:

- Target ulcer or any other ulcer on the study limb involves exposure of tendon, muscle, or bone.
- Target ulcer is of non-venous etiology (sickle cell anemia,

- necrobiosis lipoidica diabetorum, pyoderma, malignancy).
- Treatment of the target ulcer with living cellular therapy within 30 days of the time of projected randomization.
  - Endovenous ablation or other venous surgery within two weeks of enrollment
    - Venous ultrasound must be completed after procedure to determine whether there is still venous insufficiency at the time of enrollment.
  - History of skin sensitivity to any of the components of AT, multi-layer bandages or compression garments.
  - History of an acute deep vein thrombosis (DVT) or pulmonary embolism (PE) within the last three (3) months.
  - Acute thrombophlebitis within the last six (6) weeks.
  - History of pulmonary edema or decompensated congestive heart failure within six (6) weeks of screening.
  - Currently has an active infection of the skin on the target limb such as cellulitis requiring antibiotics.
  - History of target limb cancer within the last two years with the exception of treated non-melanoma skin cancer unless ulcer biopsy performed at screening is negative for neoplasia.
  - Active cancer receiving chemotherapy and/or radiation therapy.
  - Poorly controlled diabetes with an HbA1c value of > 12% within the past three (3) months.
  - Changes to medications that affect edema within the last 30 days prior to enrollment (e.g. diuretics, calcium channel blockers of the dihydropyridine class, pioglitazone, cox-1 inhibitors, pregabalin, and gabapentin, diltiazem or fluctuating doses of systemic steroids).
  - Use of systemic corticosteroids requiring daily administration at doses greater than 5mg of Prednisone per day or equivalent for greater than two weeks.
    - Low dose steroid administration (Prednisone up to 5mg per day or equivalent) is allowable for an unlimited period of time. Topical steroid administration to peri-ulcer area or other skin is allowable but cannot be applied to the ulcer itself.
  - Currently pregnant or trying to become pregnant.
  - Inability or unwillingness to participate in all aspects of study protocol.
  - Exhibit any condition which, according to the Investigator, justifies the subject's exclusion from the study, such as a medical condition where an increase in venous or lymphatic return is undesirable.
  - Currently participating in another clinical trial.

5.2.3 Additional Exclusions after two week run-in: Subjects will exit the study if they meet any of the following criteria:

- Subject's target ulcer has decreased in size by greater than 30% compared to the baseline area.
- Subject's target ulcer has increased in size by greater than 50% compared to the baseline area.
- Subject's target ulcer measures less than 1.5cm^2 at the Randomization Visit.
- Subject appears to have evidence of infection in any ulcer.
- The sum of the ulcer areas on the subject's study limb is > 50cm^2.

5.2.4 Subject Withdrawal or Early Termination:

Subjects will exit the study if they meet any of the following criteria:

- Subject death
- Subject voluntarily withdraws or investigator's decision
- Subject experiences an adverse event that in the investigator's clinical judgment necessitates study discontinuation
- Ulcer recurrence during the 3 month follow up period
- Subject acquires any of the exclusion criteria, except
  - If subject acquires an infection, they may be treated for the infection and continue in the trial in the investigator's discretion. The investigator can instruct the subject to cease sustained or IPC treatment for up to two (2) consecutive weeks but no more than four (4) weeks total. If the subject is required to abstain from study treatment for greater than the amount described above, the subject will be removed from the study.

5.3 Dosage:

Run-in

All subjects will participate in a two week run-in phase. The treatment will include multi-layer compression bandaging which must be worn 24 hours a day except during clinic visits. The run-in phase is intended to assess the subject's initial response to standard of care treatment using multi-layer bandaging before receiving treatment with the investigational device.

VLU Treatment Period

All subjects enrolled will be randomized into either treatment using the ACTitouch system or multi-layer bandaging which consists of either PROFORE or Coban 2.

Investigational Group: Subjects assigned to the ACTitouch system must wear the device in sustained mode during all wakeful hours (at least 12 hours each day) and IPC mode for a minimum of 2 hours each day. Subjects will be instructed to remove the ACTitouch for bathing and when driving or operating machinery, and reapply immediately after these activities.

At each visit the subject’s compliance will be evaluated via the compliance tracker on the ACTitouch device.

Subjects randomized to the ACTitouch arm of the study will also be contacted weekly between study visits by study personnel to support device compliance and answer questions as outlined in Section 7.16.

Control Group: Subjects assigned to multi-layer bandaging must wear the bandaging 24 hours a day except during clinic visits when the limb is being assessed by the study staff.

Follow Up Period

All subjects assigned to the ACTitouch arm who heal during the 16 week treatment period will be followed for 3 months post VLU healing. These subjects will be instructed to continue to use the ACTitouch device as outlined in the 16 week treatment period [sustained mode during all wakeful hours (12 hours each day) and IPC mode for 2 hours daily]. Subjects will be instructed to remove the ACTitouch for bathing and when driving or operating machinery, and reapplied immediately after these activities.

5.4 Study Timetable:

Task	Months				
	1-6	7-12	13-18	19-24	24-30
Identify Sites	X				
IRB/Regulatory	X				
Enrollment		X	X		
Treatment		X	X	X	X
Data Entry		X	X	X	X
Data Analysis					X

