8.3 Efficacy Analyses

All analyses will be carried out on the ITT population.

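### Section 5.2.4 ends study participation, not only study treatment, on events that can reflect ulcer outcome or intolerance, so the ITT analysis may lack those subjects' week-16 areas

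*Protocol*

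**What the plan says.** Protocol section 5.2.4 opens its list with "Subjects will exit the study if they meet any of the following criteria". Apart from death and voluntary withdrawal, the list includes an adverse event that the investigator judges to need study discontinuation, and "Subject acquires any of the exclusion criteria, except" for infection. An infected subject may stay, with treatment suspended "for up to two (2) consecutive weeks but no more than four (4) weeks total". Past that limit the rule is again exit: "If the subject is required to abstain from study treatment for greater than the amount described above, the subject will be removed from the study".

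The exclusion list in section 5.2.2 is mixed. It contains "Target ulcer or any other ulcer on the study limb involves exposure of tendon, muscle, or bone" and "History of skin sensitivity to any of the components of AT, multi-layer bandages or compression garments", and also pregnancy, an HbA1c limit and participation in another trial.

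The primary endpoint (section 12.3.1) is percent reduction in ulcer area at week 16. Section 12.5 defines ITT as everyone randomized, and SAP section 8.3 states "All analyses will be carried out on the ITT population". Section 12.6.2 expects gaps from early withdrawal and lists three approaches: complete cases, multiple imputation by linear regression on treatment and the analysis covariates, and a mixed model on available measurements. SAP section 8.3.1 names a linear mixed model for the primary analysis, and the shell for its results table (14.2.3) is labelled as an available-case population.

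**The concern.** The protocol does not distinguish a subject who stops study compression from one who leaves follow-up. A subject whose ulcer deepens, who cannot tolerate the compression materials, or whose infection keeps treatment suspended too long leaves the study altogether. The visit descriptions in section 6 contain no assessment after exit. An ITT analysis needs exactly the week-16 area that the rule gives up, and in part of these cases the reason for the gap is related to the missing value.

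The primary claim is non-inferiority against a margin of −0.125. If outcome-related exits are more frequent on ACTitouch, the difference among those still observed is too favourable to the device, and the chance of a false non-inferiority claim rises. The trial is open label. The pause limit names the two ACTitouch modes without saying how it applies to bandaging, and the two arms have different visit schedules. There is therefore no assurance that exits will be balanced.

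**Working it through.** **Does the rule remove week-16 data?** Three places, set side by side:

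- Section 5.2.4: the listed events end participation in the study.
- Section 6: treatment visits run to week 16 or healing. Unscheduled visits, follow-up after healing and recurrence visits are described, but no visit after exit.
- Section 12.5 and SAP section 8.3: all randomized subjects are analysed.

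Followed as written, an exited subject is in the ITT population without a week-16 area.

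**Do the planned analyses repair it?**

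- Complete case: leavers are dropped.
- Multiple imputation: the model described in section 12.6.2 holds treatment group and the baseline covariates (ulcer duration, ulcer size, diabetes, age). Ulcer areas measured after randomization are not listed, so a leaver is imputed like a stayer with the same baseline.
- Mixed model: areas recorded before exit can enter, which helps as far as they predict the unseen value. The SAP does not say which visits enter, and its table shell shows only baseline and week 16.

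**How large could it be?** The plan states no figure to reproduce here. The public text shows no SD, power or dropout assumption, which is not counted against the plan. Inputs from the documents: margin 0.125, one-sided alpha 0.025, 102 per arm. Assumed inputs: exit rates d, the gap g by which leavers' true week-16 reduction falls short of stayers' (equal in both arms), and the SD.

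If stayers in an arm average s, all randomized subjects in that arm average (1 − d)·s + d·(s − g) = s − d·g. Stayers therefore overstate their arm by d·g, and for the complete-case difference

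bias = g × (d_ACTitouch − d_bandage).

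Type I error at a true difference of −0.125 is 1 − Φ(1.96 − bias/SE), with SE = SD × √(1/n_T + 1/n_C) and n the number still observed.

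The SD of 0.32 is an assumption. It is close to what 102 per arm would imply at 80% power without dropout: 0.125 × √(102/2) / (1.960 + 0.842) = 0.319. With exits of 10% and 5%, n = 91.8 and 96.9, so SE = 0.32 × √(1/91.8 + 1/96.9) = 0.0466.

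| Exit, ACTitouch vs bandage | Gap | Bias | Share of margin | Type I error |
|---|---|---|---|---|
| 10% vs 5% | 30 points | 0.30 × 0.05 = +0.015 | 12% | 0.051 |
| 10% vs 5% | 50 points | 0.50 × 0.05 = +0.025 | 20% | 0.077 |
| 10% vs 5% | 80 points | 0.80 × 0.05 = +0.040 | 32% | 0.135 |
| 5% vs 5% | any, equal | 0 | 0% | 0.025 |
| 5% vs 10% | 30 to 80 points | −0.015 to −0.040 | 12–32%, against ACTitouch | below 0.025 |

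For 10% vs 5% with a 50-point gap, the type I error is 0.101 at SD 0.25 and 0.063 at SD 0.40.

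**The case against.** The strongest reply is that few exits would be ulcer failures and that the plan already has a tool for them. Much of this stands.

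- Pregnancy, HbA1c and joining another trial have nothing to do with healing. Of the exclusion criteria, exposed tendon, muscle or bone is the one clear ulcer failure. Skin sensitivity is intolerance, and prolonged infection is plausibly related to outcome.
- The mixed model uses areas recorded before exit, and ulcers are traced at every study visit (section 7.9). The bias figures above describe the complete-case contrast, and the mixed model could be less biased.
- The schedule of activities cannot be read in the public copy, and the SAP is an abbreviation of a longer one. An assessment at termination cannot be ruled out, although an early one would not be a week-16 value.

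A reader might also infer more than the documents support:

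- *That ulcer growth above 50%, or a summed area above 50 cm², triggers exit during treatment.* These are post-run-in criteria in section 5.2.3, and section 6.2 applies them at the Randomization Visit. Carried past randomization, the same list would also expel ulcers that shrink by more than 30% or fall below 1.5 cm², which are the responders.
- *That a change in edema medication or decompensated heart failure is a sure trigger.* Section 5.2.2 dates these relative to enrollment and screening, so read literally they cannot be acquired later.
- *That any long treatment pause leads to exit.* The limit is written only within the infection exception.
- *That the bias must favour ACTitouch.* The documents give no exit rates by arm, and the sign depends on which arm loses more.

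What remains is that no listed analysis treats leavers as poor outcomes or tests how far the result depends on them, and that the measurement itself is given up by rule.

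**Conclusion.** The point holds in a limited form. As written, section 5.2.4 turns some treatment-stopping events into loss of follow-up. Some of those events plausibly relate to ulcer outcome or intolerance, and the visible text provides no week-16 measurement afterwards. Complete-case analysis and covariate-only imputation do not address this, and the mixed model does so only in part.

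The size is illustrative. Under assumed exits of 10% on ACTitouch and 5% on bandaging and gaps of 30 to 80 points, a complete-case contrast is biased by +1.5 to +4.0 points, or 12–32% of the margin. With an assumed SD of 0.32, the one-sided type I error is then 0.051 to 0.135 instead of 0.025. Balanced exits with equal gaps give no bias, and more exits on bandaging push the result against the device. The plan should be changed because the exposure is avoidable at little cost, not because a particular bias has been shown.

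**What to change.** In section 5.2.4, separate two states: stopping study treatment, and withdrawing from the study. Leave every treatment-stopping rule as it is. State that a subject who stops treatment remains in follow-up, and that unless the subject has died or withdrawn consent, the already-scheduled week-16 photograph and tracing are obtained and used in the ITT analysis. Wherever the image is obtained, the bias term above disappears. While the section is open, say how the pause limit, which is worded in ACTitouch modes, reads for the bandage arm.

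Some subjects will still withdraw consent. For them, a delta-adjusted or tipping-point sensitivity analysis against −0.125 would show how poor their outcomes must be to change the conclusion.

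The cost is protocol wording and one already-planned visit for a small number of subjects. In the 10% vs 5% illustration, that is about 10 + 5 = 15 of 204. The sensitivity analysis needs no new data.
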